E-cigarettes present a potential innovative solution to the challenges of reducing tobacco smoking among adults with SMI. E-cigarettes provide an experience close to tobacco smoking, which may increase their acceptability and use. The long-term health consequences of e-cigarette use are unknown. However, no negative health consequences of short-term use as in the current study have been reported, and most researchers agree that e-cigarettes are likely healthier than tobacco smoking¹⁷. Importantly, two small open-label studies observed decreased tobacco smoking among non-treatment seeking adults with schizophrenia and schizoaffective disorder following one month of access to e-cigarettes^{18,19}. Such results are promising as individuals with schizophrenia exhibit severe tobacco smoking, even when compared to others populations with SMI.

In the current pilot proposal, adults with SMI (N=10/group) interested in reducing their tobacco smoking will be randomized to receive either nicotine replacement therapy (NRT; patch 21 mg) as the standard of care or NRT plus e-cigarettes (36 mg/ml) for one month according to a double-blind, randomized controlled trial design. We will use a previously evaluated e-cigarette including nicotine liquid solutions that have been independently tested.

SPECIFIC AIMS AND HYPOTHESES

Specific Aim 1: Assess feasibility, acceptability, and safety of providing e-cigarettes to adults with SMI to reduce tobacco smoking.

Hypothesis 1.a: *We predict that a high proportion of participants will consent to participate ($\geq 80\%$) and complete ($\geq 70\%$) the study.*

Hypothesis 1.b: *We predict that end of study participant satisfaction ratings will indicate high acceptability of e-cigarettes and likelihood of future use.*

Hypothesis 1.c: *We predict e-cigarettes will be safe as measured by frequency of adverse events (AEs) and side-effects. In addition, we predict e-cigarettes will not be associated with increases in symptom specific measures.*

Specific Aim 2: **To compare reductions in tobacco smoking between NRT vs NRT + e-cigarettes (36 mg/ml).**

Hypothesis 2: *Significantly greater reductions in smoking (tobacco cigarettes/day, breath CO) will be observed in the NRT + e-cigarette vs. the NRT condition.*

BACKGROUND AND RATIONALE

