Study Design and Overview. We will utilize a double-blind, randomized controlled design to assess the feasibility and acceptability of using e-cigarettes to reduce tobacco smoking among individuals with SMI (schizophrenia and schizoaffective disorder, bipolar disorder, or PTSD). Participants will consist of tobacco smokers with SMI interested in reducing or quitting their tobacco smoking. Note that these two experimental conditions were chosen based on available funds and likelihood of obtaining preliminary data that would be useful in a future NIH grant application. We plan to assess other conditions in the future (e.g., placebo e-cigarette, etc.). Following a one-week baseline lead-in period, participants will be randomized to either the NRT or NRT + e-cigarette condition. Study visits will be scheduled for once a week (5 weeks total).

[figure not shown]

Figure 1. Overview of study design.

Study Procedures and Assessments

Participant Recruitment and Selection. Participants will be recruited from the ICNTP, PIRL-M, and STARS clinic. Eligible participants will meet the following inclusion criteria: 1) be diagnosed with schizophrenia or schizoaffective disorder, bipolar disorder, or PTSD and in stable medical condition (DSM-5); 2) report smoking ≥ 10 tobacco cigarettes/day and present a breath CO ≥ 10 ppm; 3) report wanting to quit or reduce their cigarette smoking; 4) be fluent in English; 5) be between 18 and 65 years of age; and 6) have a stable living situation. Participants will be ineligible if they meet the following exclusion criteria: 1) be currently pregnant or breastfeeding; 2) report wanting to quit smoking in the immediate future; 3) test positive for illicit drugs except THC; and 4) have any illness, medical condition, or use of medications, which in the opinion of the study physicians (Drs. [name] and [name]) would preclude safe and/or successful completion of the study.

Following informed consent, participants will complete an initial general evaluation protocol (HSC-MS-05-0322; General evaluation of Eligibility for Substance Abuse/Dependence Research) to assess their psychiatric status, medical evaluation, and drug use history.

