E-cigarette. The e-cigarette will consist of 1) a 3.3 V, 1000 mAh battery; and 2) a 1.5 Ohm, dual-coil cartomizer (SmokTech; Shenzhen, China). Study staff will load the cartomizer with 1 ml tobacco flavored 70% propylene glycol/30% vegetable glycerin liquid containing nicotine concentrations 36 mg/ml (AVAIL; Richmond, Virginia, USA). Nicotine concentration will be tested at an independent laboratory at VCU (± 2 mg/ml). Virtually every aspect of the e-cigarette (model, voltage, resistance, liquid, and nicotine concentration) has been chosen based on systematically conducted studies by [name] and his colleagues³⁸⁻⁴¹. With these parameters, e-cigarettes with 36 mg/ml nicotine liquid produce blood plasma nicotine levels similar to that of tobacco cigarettes after 10 puffs. Participants will be provided verbal and written instructions on how to use and maintain the e-cigarettes at Week 1 visit. Risking of spilling nicotine liquid is minimal as the cartomizer contains cotton batting for liquid absorption. However, to mitigate any potential risks, participants will be provided gloves to be used when changing cartomizers. Additionally, they will receive pill bottles to hold spare cartomizers, instructed not to try and open the cartomizer, and told to keep them away from children.

Nicotine Replacement Therapy. Participants will receive nicotine patch (21 mg) starting study Week 1. Participants will be instructed to apply a new patch each morning on a clean, dry, non-hairy area of skin.

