E-Cigarette and Tobacco Smoking Related Assessments. Tobacco smoking will be assessed using a combination of breath CO, urinary cotinine, and self-report via time-line follow-back. Standard questionnaires will be used to assess a number of tobacco-smoking related measures. The Fagerstrom Test for Nicotine Dependence (FTND) will be used to assess tobacco cigarette dependence⁴². The Questionnaire of Smoking Urges (QSU) will be used to assess craving for tobacco cigarettes⁴³. The Minnesota Nicotine Withdrawal Questionnaire (MNWQ) will be used to assess withdrawal symptoms from tobacco cigarettes⁴⁴. The Stages of Change Questionnaire will be administered to assess desire to quit from tobacco cigarette smoking⁴⁵. The Clinical COPD Questionnaire (CCQ) will be used to assess changes in COPD-related symptoms⁴⁶. Additional smoking-related assessment will include the Confidence to Quit (CQ) and Hooked on Nicotine Checklist (HONC). E-cigarette related questionnaires developed and provided by [name] will be used to evaluate e-cigarette dependence, patterns of use, evaluation of using e-cigarettes, and side-effects. These questionnaires will include Confidence to Quit, E-Cigarette Dependence Scale, E-Cigarette Patterns of Use, E-Cig Evaluation, E-Cig Side Effects, and Hooked on Nicotine Checklist.

Assessing Changes in Symptoms Relevant to SMISchizophrenia. The Brief Psychiatric Rating Scale (BPRS)⁴⁷ will assess symptom severity among individuals with SMI. Potential changes in key cognitive domains associated with will be assessed with the MATRICS Consensus Cognitive Battery (MCCB). The Columbia Suicide Severity Rating Scale (CSSRS) will assess suicide ideation. Changes in mood symptomatology including also anhedonia and mania will be assessed with the Beck Depression Inventory (BDI), Snaith-Hamilton Pleasure Scale (SHAPS), and the Altman Self-Rating Mania Scale (ASRM) respectively. Changes in PTSD symptoms will be assessed using the PTSD Checklist for DSM 5.

Safety and Health-Related Measures. Adverse events (AEs) and severe AEs, along with concomitant medications, will be assessed at weekly study visits. Heart Rate (HR) and blood pressure (BP) will also be assessed using standard hospital-grade equipment.

Table 1. Outline of Study Procedures and Assessments.

Procedure and Assessments	Study Visits	Week 0	Week 1	Week 2	Week 3	Week 4	Week 5
Baseline Screening		X					
Receive E-Cigarettes (36 mg/ml) and NRT Patch (21 mg)				X	X	X	X
Smoking Related Assessments							

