Breath CO, QSU, MNWQ, , TLFB, CCQ, CQ, HONC		X	X	X	X	X	X
Urinary Cotinine		X					X
FTND, Stages of Change		X					X
E-Cigarette Questionnaires				X	X	X	X
AEs, Concomitant Meds, HR, BP		X	X	X	X	X	X
BPRS, CSSRS, BDI, SHAPS, ASRM, PTSD		X	X	X	X	X	X
MCCB		X					X

DATA ANALYSIS PLAN

Preliminary data analyses will inspect baseline, group differences as well as correlations between baseline variables and specified outcomes. Baseline or demographic variables demonstrating a correlation with both predictors and outcomes, meet criteria for being potential confounders,^{i,ii} and will result in two sets of analyses: one in which the relevant variable is included as a covariate and one in which it is not. This will determine the degree to which any group differences might confound conclusions regarding treatment. Statistical analyses will use R v. 3.3.0ⁱⁱⁱ and SAS v.9.3.^{iv}

Analyses will primarily use generalized linear modeling. Continuous, count, dichotomous and time-to-event data will utilize linear, Poisson, logistic, and proportional hazards regression respectively (Proc GENMOD and PROC PHREG; SAS v. 9.3, function glm(); R v. 3.3.0). Longitudinal analyses will employ generalized linear mixed models (Proc MIXED, Proc GLIMMIX and Proc MCMC; SAS 9.3). Evaluation of distributional assumptions will use residual plots and, where possible, formal statistical tests. Depending upon statistical technique, transformations, robust estimators, stratification and/or scaling coefficients will address violations of assumptions. Analyses of cross-sectional data with missing values will utilize multiple imputation (Proc MI; SAS v.9.3)^v. Multiple imputation and maximum likelihood are robust to data missing at random. Sensitivity analyses will permit evaluation of the robustness of findings to missing data assumptions.

Specific Aim 1: Assess feasibility, acceptability, and safety of providing e-cigarettes to adults with SMI to reduce tobacco smoking.

Hypothesis 1.a: We predict that a high proportion of participants will consent to participant (80%) and complete the study (70%) completion rate. Descriptive statistics will evaluate consent and completion rates.

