Results from the current pilot study will be used as preliminary data in support of a future NIH R21 grant submission. The immediate goal of that R21 will be to assess a longer intervention period (3 months), which is the standard in clinical trials, as well as additional experimental conditions (e.g., 0 mg/ml e-cigarette condition) to enhance the experimental rigor of the study. Based on the current results, we will also assess the need for additional intervention components (e.g., contingency management, motivational interviewing, etc.). Finally, we will also assess other indices of reduced tobacco smoking toxicity such as 4-methylnitrosamino-1-3-pyridyl-1-butanol (NNAL) and lung function using spirometry. The R21 will in turn lead to a future R01 application. Additionally, completion of the current proposal will also be beneficial in establishing a history of cooperation with Drs. [name], [name], [name], and [name] that will also support the competitiveness of future NIH grant submissions on which they serve as collaborators.

CITATIONS

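### The trial is labelled double-blind, but with a patch-only arm and no sham device participants cannot be blinded, so self-reported cigarettes/day and the reported or rated safety outcomes are open to bias from known allocation

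*Combined protocol and SAP*

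**What the plan says.** The blinding claim appears twice. The opening proposal paragraph, before Specific Aims and Hypotheses, describes "NRT plus e-cigarettes (36 mg/ml) for one month according to a double-blind, randomized controlled trial design". METHODS, Study Design and Overview, repeats it: "We will utilize a double-blind, randomized controlled design to assess the feasibility and acceptability".

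The comparator arm receives the 21 mg patch; the other arm receives the patch and the e-cigarette. On a sham, Study Design and Overview says "We plan to assess other conditions in the future (e.g., placebo e-cigarette, etc", and JUSTIFICATION reserves for the later R21 "additional experimental conditions (e.g., 0 mg/ml e-cigarette condition) to enhance the experimental rigor of the study". On handling, the E-cigarette section says "Study staff will load the cartomizer with 1 ml tobacco flavored" and "Participants will be provided verbal and written instructions on how to use and maintain the e-cigarettes at Week 1 visit". It also provides gloves and storage bottles for spare cartomizers.

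On measurement: "Tobacco smoking will be assessed using a combination of breath CO, urinary cotinine, and self-report via time-line follow-back". The Table 1 row "Breath CO, QSU, MNWQ, , TLFB, CCQ, CQ, HONC" is marked at every visit, Weeks 0 to 5; urinary cotinine is marked at Weeks 0 and 5 only. Hypothesis 2 names cigarettes/day and breath CO and gives each its own model (Poisson and Gaussian). It does not say whether both must show a difference, or how a difference on cigarettes/day alone would be read. Hypothesis 1.c relies on adverse events, side-effects, the BPRS and cognitive performance.

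**The concern.** A double-blind label tells the reader that knowledge of treatment did not shape behaviour, reporting or rating. This two-arm design cannot deliver that for participants. Everyone enrolled has said they want to quit or reduce. Someone handed a device meant to replace cigarettes may report fewer cigarettes than were smoked, and someone left with the patch alone may misreport by a different amount or in the other direction. Either would create or distort a group difference in cigarettes/day.

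The same knowledge can affect Hypothesis 1.c, where side-effects are self-reported and psychiatric symptoms are reported or rated.

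The Abstract and JUSTIFICATION say the results are meant to support an NIH application. What the pilot can be said to show depends on an accurate description of who was blinded.

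**Working it through.** **Label against design.**
1. Stated property: double-blind, in two places.
2. Arms: patch versus patch plus a hand-held device. No sham is described for the patch-only arm, and both mentions of a placebo or 0 mg/ml device place it in future work.
3. Device-arm participants are trained on the device and handle it. Patch-only participants do not receive one. Each participant therefore knows the allocation, and so does whoever dispenses the device.
4. Some Methods text and Figure 1 were not available for this review. They could describe masked raters or analysts. They could not make participants blind with these two arms.

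**Which outcomes are exposed.** Cigarettes/day comes from time-line follow-back, which is self-report. Breath CO is a physical measurement, although real behaviour that changes because the arm is known would still show in it. Urinary cotinine cannot settle a disagreement between the two, because both arms receive nicotine from a non-tobacco source and one arm receives a second such source.

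**The plan's own figure.** Power/Sample Size Considerations gives 80% power at f = 0.51, N = 20, alpha 0.05, correlation 0.5. The number of repeated measures m is not stated. For a repeated-measures between-group F test with 1 and 18 df, the noncentrality is λ = f²·N·m / (1 + (m − 1)·0.5).
- m = 5: λ = 0.2601 × 20 × 5 / 3 = 8.67, power 79.5%.
- m = 6: λ = 0.2601 × 20 × 6 / 3.5 = 8.92, power 80.6%.

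The stated 80% reproduces at m = 5 or 6. It makes no allowance for reporting bias.

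**Illustration of bias on cigarettes/day alone.** Assumptions: no true effect; a constant extra under-report of b cigarettes/day in the device arm; two-sided alpha 0.05; SD taken from the reductions 9.9 ± 7.0 and 5.7 ± 6.3 quoted in the Background, reading ± as SD. That contrast is e-cigarette versus NRT, not this trial's. The values of b are assumed, since the documents give none.

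Pooled SD = √((7.0² + 6.3²)/2) = 6.66.

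*Single change score, two-sample t-test:* noncentrality = (b/6.66)·√(n/2), df = 2n − 2.

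*Repeated-measures between-group test:* f = (b/6.66)/2 in the formula above, m = 4 to 6, 10 per arm, treating 6.66 as the per-visit SD.

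| Assumed b (cigarettes/day) | t-test, 10 per arm | Repeated measures, 10 per arm | t-test, 7 per arm |
|---|---|---|---|
| 1 | 6.2% | about 7% | 5.8% |
| 2 | 9.8% | about 13% | 8.1% |
| 3 | 15.9% | 23-24% | 12.2% |

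With 10 per arm, the t-test noncentralities are 0.336, 0.672 and 1.007. The last column applies the predicted 70% completion (0.7 × 10 = 7) to completers only. With SD between 7.0 and 6.3, the t-test figures at 10 per arm are 6.1-6.3%, 9.3-10.3% and 14.9-17.2%.

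For scale, the quoted Background difference is 9.9 − 5.7 = 4.2, so b = 1, 2, 3 is 24%, 48% and 71% of it. Biases of 2 or 3 would be large. The planned model for cigarettes/day is Poisson, so these Gaussian figures are approximate.

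**If Hypothesis 2 needs both outcomes.** P(both significant) ≤ P(breath CO significant), which is 5% when there is no true effect on CO. Under-reporting alone cannot then raise the joint error above 5%.

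**The case against.** The best defence is that little is hidden and much is already mitigated. The arms are described in the same sentence as the label, and the absence of a placebo device is acknowledged. Breath CO stands beside cigarettes/day in Hypothesis 2, has its own model and is taken at every visit. The Background already reads reported smoking reduction together with CO. This is a pilot, its first aim is feasibility, acceptability and safety, and efficacy is left to a full-scale trial. All of this stands, and it limits the consequence. It does not make the label true. Aim 2 still predicts a significant difference, the power statement is built on Aim 2, and no rule covers a result on cigarettes/day alone.

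The false-positive figures are also open to attack: they depend on invented bias sizes, a borrowed SD, the choice of test and the number analysed. That is correct, and they are illustrative only. A reader might infer from them that this trial's error rate is 16% or 24%. The documents do not support that, because they give neither the size nor the direction of any bias.

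A reader might also infer that nobody is masked. That cannot be concluded either, since text describing masked raters or analysts may exist in the parts not available.

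**Conclusion.** The point holds. The plan states a property that its design lacks: participants, and staff who dispense the device, cannot be blinded. This conclusion needs no assumption about bias and would stand if the bias were zero.

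The consequence is moderate. Cigarettes/day and the self-reported or rated parts of Hypothesis 1.c are exposed to known allocation; breath CO is not exposed to misreporting. Under the assumptions above, a bias of 1 cigarette/day has little effect on the error rate for cigarettes/day, and only biases that are large against the quoted 4.2 difference raise it substantially.

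It would go too far to say that Aim 2 is invalid. An outcome independent of self-report sits within the same hypothesis. The description should be corrected, but the trial's conduct and Aim 1 are not invalidated.

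**What to change.** 1. In the opening proposal paragraph and in Study Design and Overview, replace the double-blind wording with 'randomized, open-label to participants'. Add one sentence saying who, if anyone, is masked, consistent with any masking text already in the protocol. Use 'assessor-blinded' only if it is true.

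2. In Hypothesis 2, under both Specific Aims and the Data Analysis Plan, state that cigarettes/day is an unblinded self-report. Its group difference and 95% confidence interval will be reported beside those for breath CO, and a difference not supported by breath CO will be described as self-reported, not biochemically supported, reduction. Say in advance what counts as support. Agreement in the direction of the point estimate would occur about half the time by chance if there were no CO effect and the errors were independent; requiring significance is strict at 10 per arm. Showing both intervals lets readers judge. Making breath CO the lead outcome is optional.

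3. Report unblinded participants as a limitation for Hypothesis 2 and Hypothesis 1.c. Include the possibility that knowing one's arm changes real behaviour, which breath CO does not remove.

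The cost is a few sentences, with no new visits, assays or participants. The downside is that the double-blind label is lost and a result seen only in self-report supports a weaker claim.

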Hypothesis 1.b: We predict that end of study participant satisfaction ratings will indicate high acceptability of e-cigarettes and nicotine patch and likelihood of future use. Generalized linear models will evaluate the relationships between participant satisfaction, acceptability of e-cigarettes and nicotine patch, and likelihood of future use.

Hypothesis 1.c: We predict e-cigarettes will be safe as measured by frequency of adverse events (AEs) and side-effects, and not associated with increases in negative symptoms (BPRS) or decreases in cognitive performance (MATRICS). Generalized linear modeling will evaluate relationships between adverse events/side-effects, negative symptoms, and cognitive performance.

Specific Aim 2: To compare reductions in tobacco smoking between NRT vs NRT + e-cigarettes (36 mg/ml).

Hypothesis 2: *Significantly greater reductions in smoking (tobacco cigarettes/day, breath CO) will be observed in the NRT + e-cigarette vs. the NRT condition. Generalized linear modeling will evaluate group differences in smoking reduction between NRT and NRT + e-cigarettes over time as measured by breath CO (using a Gaussian distribution) and tobacco-cigarettes/day (using a Poisson distribution).*

Power/Sample Size Considerations. For the current proposal, power will focus on Aim 2. Effect size is derived using G*Power 3.1.9.2. Assuming alpha = 0.05 and a correlation among repeated measures of 0.5, a sample size of n = 20 (n = 10 NRT and 10 NRT + e-cigarette) provides 80% power to detect a Cohen's f = 0.51 for group differences between NRT and NRT + e-cigarette. The Frequentist findings will be augmented with a Bayesian approach to characterize the probability that effect sizes of varying magnitude exist.

JUSTIFICATION

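### Hypothesis 2: the only covariate rule ties baseline adjustment to chance imbalance and names no primary result; pre-specified baseline adjustment is a near-free, modest gain in precision (minor)

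*Combined protocol and SAP*

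**What the plan says.** The Data Analysis Plan sets one rule for covariates: "Baseline or demographic variables demonstrating a correlation with both predictors and outcomes, meet criteria for being potential confounders". A variable that meets it leads to "two sets of analyses: one in which the relevant variable is included as a covariate and one in which it is not". The stated purpose is a confounding check: "This will determine the degree to which any group differences might confound conclusions regarding treatment". The plan does not say how large a correlation must be, or which of the two analyses carries the conclusion.

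Under Specific Aim 2, the Hypothesis 2 analysis reads "Generalized linear modeling will evaluate group differences in smoking reduction between NRT and NRT + e-cigarettes over time", with a Gaussian model for breath CO and a Poisson model for cigarettes/day. No baseline covariate is named. The text does not say whether pre-product visits enter as outcomes, as the reference for a change score, or as a covariate.

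Allocation is random: "Following a one-week baseline lead-in period, participants will be randomized to either the NRT or NRT + e-cigarette condition". Table 1 schedules breath CO and the timeline follow-back at Weeks 0 to 5, which is six visits.

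**The concern.** The rule has two halves. Correlation with the outcome selects prognostic variables, which is useful. Correlation with the predictors, which include the arm, selects variables that happen to be unbalanced. In a randomised trial that imbalance is chance, so the rule withholds adjustment from a strongly prognostic baseline whenever the arms are balanced on it. Yet the precision gained by adjustment comes from the link between baseline and outcome, and does not require imbalance.

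Two things are at stake. First, with 20 participants, some precision on Aim 2 is given up, although the Justification section intends the results as preliminary data for a grant application. Second, when the rule does fire, two results stand and the reader is not told which one answers Hypothesis 2.

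**Working it through.** **Inputs.** From Power/Sample Size Considerations: "Assuming alpha = 0.05 and a correlation among repeated measures of 0.5", 10 per arm, 80% power at Cohen's f = 0.51. With two equal groups d = 2f = 1.02 on the single-visit SD. From Hypothesis 1.a: "complete the study (70%) completion rate", so 0.70 × 20 = 14 completers for a sensitivity run. Assumptions: one common correlation ρ between all visits, complete data, Gaussian breath CO.

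**The plan's own figure.** For a between-group test on the average of m visits, λ = f²·N·m / (1 + (m−1)ρ), with 1 and 18 degrees of freedom. The number of visits is not stated.
- m = 5: λ = 0.2601 × 20 × 5 / 3 = 8.67, power 79.5%.
- m = 6: λ = 0.2601 × 20 × 6 / 3.5 = 8.92, power 80.6%.

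So f = 0.51 reproduces, as a test of a visit average without baseline adjustment.

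**Layouts.** The Nicotine Replacement Therapy section starts the patch at Week 1, and Table 1 marks product receipt at Weeks 2 to 5. Three layouts follow:
- Weeks 0–1 before product and Weeks 2–5 on product (2/4).
- Weeks 0–2 before and Weeks 3–5 on product (3/3).
- Weeks 0–1 as baseline and Weeks 3–5 on product (2/3), if Week 2 is pre-product but set aside because it follows randomisation.

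**Formulas,** with a pre-product and b on-product visits and single-visit variance 1:
- pre-product mean: vp = (1 + (a−1)ρ)/a
- on-product mean: vq = (1 + (b−1)ρ)/b
- change: vp + vq − 2ρ
- adjusted for the pre-product mean: (vq − ρ²/vp) × (1 + 1/(N−4)); the last factor is 1.0625 at N = 20 and 1.10 at N = 14
- CI ratio: √(adjusted/change) × t(N−3)/t(N−2); the t values are 2.110 and 2.101 at N = 20.

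**Worked case, 2/4, ρ = 0.5, N = 20.** vp = 0.75 and vq = 0.625. Change = 0.75 + 0.625 − 1 = 0.375. Adjusted = (0.625 − 0.25/0.75) × 1.0625 = 0.2917 × 1.0625 = 0.310. The variance cut is 1 − 0.310/0.375 = 17%. The CI ratio is √0.826 × 2.110/2.101 = 0.913. Power uses the noncentral t with δ = 1.02/√(2V/10): 94% for change and 97% for adjusted.

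| Layout | Change | Adjusted | Variance cut | CI narrower | Power at f = 0.51 | CI narrower, 14 completers |
|---|---|---|---|---|---|---|
| 2/4 | 0.375 | 0.310 | 17% | 9% | 94% → 97% | 7% |
| 2/3 | 0.417 | 0.354 | 15% | 7% | 92% → 95% | 5% |
| 3/3 | 0.333 | 0.310 | 7% | 3% | 96% → 97% | 1% |

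A repeated-measures model with baseline as a response and separate arm means gives the same contrast variance as change (0.375, 0.417, 0.333), so the comparison covers both readings of Hypothesis 2.

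**Weaker comparator.** Against the on-product mean with no baseline at all (0.625, 0.667, 0.667), the variance cut is 50%, 47% and 54%.

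**Dependence on ρ.** Counting the lost degree of freedom, the CI ratio against change reaches 1 at ρ of about 0.82 (2/4), 0.80 (2/3) and 0.68 (3/3). With 14 completers and 2/4 or 3/3, it does so at about 0.72 and 0.54. For 3/3 at ρ = 0.8 and N = 20, adjustment raises the variance by about 2%.

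**Entry criterion.** Participants must "report smoking ≥ 10 tobacco cigarettes/day and present a breath CO ≥ 10 ppm". Truncating Week 0 CO weakens the baseline correlation. If the CO limit screens out 7%, 16% or 31% (assumed), the variance cut falls to 14%, 12% or 9% (2/4) and 6%, 4% or 2% (3/3).

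**How often the rule fires.** In simulated null trials at ρ = 0.5, baseline CO passes both halves in about 2–5% of trials if the cut-off is p < 0.05, 12–20% at |r| > 0.3, and 31–40% at |r| > 0.2. If a result counted as positive whenever either p-value fell below 0.05, type I error would be about 5–6%.

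**The case against.** The strongest reply is that baseline is not ignored. Hypothesis 2 concerns reduction over time, and the Data Analysis Plan assigns longitudinal data to mixed models. Pre-product smoking then enters through change or repeated measures whether or not the rule fires, and the rule is only a sensitivity check for confounding. A mixed model with a common baseline mean would also fit the text and recover much the same precision. This largely stands, and it is why change is the comparator above and why the loss is modest. It leaves two gaps: the text does not commit to an efficient use of baseline, and no primary result is named when the rule fires.

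A second reply is that this is a pilot feasibility project that reports both analyses. That also stands as to validity. It does not remove the value of precision, since the power statement is built on Aim 2.

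Three stronger readings are tempting, and the documents do not support them:
- *The rule biases the comparison or inflates false positives.* Allocation is random, and even the worst use of the two p-values stays near 5–6%.
- *About half the variance is being wasted.* That holds only if Hypothesis 2 ignores baseline altogether. The power figure is built that way, but the analysis wording points to change.
- *The gain is large because Week 0 alone is baseline.* A layout with one visit before and four after does not fit Table 1's six CO visits, and the one-week lead-in argues against a single baseline visit.

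**Conclusion.** The point holds as a minor one. The covariate rule makes explicit baseline adjustment depend on chance imbalance and an unstated cut-off, and leaves two results without a primary when it fires. At the plan's correlation of 0.5 the cost for breath CO, relative to change from baseline, is a confidence interval that could be 3–9% narrower with 20 participants, or 1–7% narrower with 14 completers. The size rests on a common correlation between visits, a Gaussian outcome, non-informative dropout in the 14-completer figures, and a ρ that is a planning value rather than an estimate. A ρ well above 0.5 would remove the gain, or turn it into a small loss. Nothing is quantified for cigarettes/day, because the documents give no baseline mean or variance for it.

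**What to change.** For Hypothesis 2, replace the correlation screen with wording such as:

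*Each model adjusts for the baseline value of the same measure (breath CO in the Gaussian model, log cigarettes/day in the Poisson model), defined as the mean of all values taken before product is first received and before the participant knows the arm, whatever imbalance is observed. This adjusted analysis is primary; unadjusted analyses and adjustment for other variables are supportive.*

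The Nicotine Replacement Therapy section (patch from Week 1) and Table 1 (receipt at Weeks 2 to 5) must be reconciled so that the pre-product visits are known. A visit that is pre-product but after randomisation counts as baseline only if the participant does not yet know the arm.

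The cost is SAP wording and one residual degree of freedom. No new data are needed, since breath CO and the timeline follow-back are already collected at every visit. The remaining risk is a small loss of precision if the true correlation is well above 0.5.
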